## 3 STUDY DESIGN

This is a single-center, open-label pilot study. All study subjects will receive both Winlevi at baseline. The duration of the study is [REDACTED] weeks and consists of a Screening, Baseline Visit, and Follow-up Visits at Weeks [REDACTED]. The treatment period is [REDACTED] weeks and [REDACTED] weeks of safety follow up totaling to [REDACTED] weeks.

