#### **4.3 Withdrawal of Subjects**

It is the right and duty of the Investigator to discontinue the study participation of a subject when the subject's health or well-being is threatened by continuation in the study. Such subjects should be withdrawn from the study.

The following are circumstances that would result in the subject's discontinuation from the study:

- the subject experiences a serious adverse event rendering them unable to continue study participation;
- the subject is unable to physically or mentally tolerate the use of the test medication;
- an exclusion criterion becomes apparent at any time during the study; or
- the subject voluntarily withdraws.

In the event of premature discontinuation from the study, the Investigator should determine the primary reason for discontinuation. A subject who is withdrawn from the study prior to initiation of treatment may be replaced.

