### **5.3 Concomitant Medication/Treatment**

Please see Supplement I for a listing of prohibited medications. Necessary therapies that will not interfere with the response to treatment may be provided at the discretion of the Investigator. The use of any concurrent medication, prescription or over-the-counter drug, is to be recorded in the CRF along with the reason the medication was taken.

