## 6 STUDY ASSESSMENTS

### 6.1 Primary Endpoint

The primary endpoint of this study is the percent of patients who achieve clear or almost clear on IGA at week 16.

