## **8 STATISTICS**

### **8.1 Sample Size Justification**

A total of 10 subjects will be entered into the study. This is a pilot study and a formal justification for the sample size is not provided. The data from this study will provide important data for determining any trends regarding the safety and efficacy of study medication.

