### **8.2 Analyses**

Statistical analyses will be conducted on an intent-to-treat basis (i.e., all enrolled subjects will be included in the analyses). All statistical tests will be two-sided and interpreted at a 5% significance level. Descriptive statistics (i.e., mean, standard deviation, etc.) will be provided for all continuous variables and frequencies for all categorical variables collected in this study. These will be presented by treatment group. Summary tables will be used to present patient population characteristics at Baseline; data from the study questionnaires will be included. The incidence and severity of adverse and/or unexpected events will be tabulated and a complete listing of all reports of adverse and/or unexpected events will be presented.

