### **10 SUPPLEMENTS**

#### **I Prohibited Medications / Wash-Out Periods**

#### **SUPPLEMENT I Prohibited Medications / Wash-Out Periods**

Use of the following medications (concurrent and contraindicated treatments) are prohibited during the course of the study and appropriate wash-out periods must be respected:

[REDACTED]	[REDACTED]

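### The week-16 IGA response has no stated rule for a subject who used another acne treatment, so clearance on that treatment would count as a Winlevi success

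*Combined protocol and SAP*

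**What the plan says.** - **Endpoint.** Section 6.1 makes the primary endpoint "the percent of patients who achieve clear or almost clear on IGA at week 16". It sets no condition on what else the subject used. The section 6.2 lesion reductions at week 16 carry no condition either.
- **Analysis set.** Section 8.2 applies intention-to-treat, under which "all enrolled subjects will be included in the analyses". It defines no second analysis set, no non-response rule and no rule for missing data.
- **Other treatment.** Supplement I says that the listed medications "are prohibited during the course of the study and appropriate wash-out periods must be respected". Section 5.3 lets the investigator provide necessary therapy only if it will not interfere with the response to treatment.
- **Record.** Under section 5.3, use of any concurrent drug, including over-the-counter products, "is to be recorded in the CRF along with the reason the medication was taken". Section 8.2 makes no use of this record.
- **Design and size.** Section 3: "This is a single-center, open-label pilot study". Section 8.1: "A total of 10 subjects will be entered into the study".

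Two places cannot be checked. The Supplement I table is redacted, and section 5.1 shows no text.

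**The concern.** The protocol treats certain drugs as liable to distort the response it wants to measure: it bans some and bars others that would interfere. Its endpoint and analysis do not say what happens to the result if a subject uses one anyway. A subject who does not respond to Winlevi, obtains an effective acne treatment and is clear at week 16 meets section 6.1.

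The study has one arm, and section 2 states its aim as observing the efficacy and safety of Winlevi. No control group exists in which added treatment would also occur and partly cancel out, so the reported percentage will be read as response to Winlevi. Subjects doing poorly have the most reason to look elsewhere. Effective added treatment can turn a failure into a success but would seldom do the reverse, so the distortion runs mainly upward.

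**Working it through.** **Inputs.** N = 10 in a single arm (section 8.1). The endpoint is a simple proportion x/10 (sections 6.1 and 8.2). The documents give no expected response rate and no rate of use of other acne treatment. There is no derived figure to reproduce, because section 8.1 states: "This is a pilot study and a formal justification for the sample size is not provided".

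**Step 1: tracing the rule.**

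| Question | Visible text |
|---|---|
| Is other acne treatment restricted? | Yes: Supplement I and 5.3 |
| Is its use recorded? | Yes: CRF, with the reason (5.3) |
| Does the endpoint depend on it? | No (6.1) |
| Does the analysis depend on it? | No (8.2) |

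The plan nowhere states that clearance on another drug is a success. That follows from an unconditional endpoint, an all-enrolled analysis and no rule to the contrary.

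**Step 2: effect of one subject.** 1/10 = 10 percentage points.

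**Step 3: illustration with assumed counts.** Suppose 3 subjects respond to Winlevi alone and 1 or 2 more clear on another acne treatment. Intervals are exact (Clopper-Pearson) 95%.

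| Responders counted | Percentage | 95% interval |
|---|---|---|
| 3 of 10 (Winlevi alone) | 30% | 6.7 to 65.2 |
| 4 of 10 (one added) | 40% | 12.2 to 73.8 |
| 5 of 10 (two added) | 50% | 18.7 to 81.3 |

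**Step 4: how the remedy is applied matters.** Suppose instead that 3 of 10 are observed clear and one of them used another acne treatment (assumed). Counting that subject as a non-responder gives 2/10 = 20% (2.5 to 55.6). Removing the subject gives 2/9 = 22.2% (2.8 to 60.0). Only the first keeps the all-enrolled denominator of section 8.2.

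**Step 5: how often it could arise.** With an assumed probability p of such use per subject, independent between subjects, P(at least one of 10) = 1 − (1 − p)^10.

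| Assumed p | P(at least one user) |
|---|---|
| 5% | 40% |
| 10% | 65% |
| 20% | 89% |
| 30% | 97% |

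These are upper bounds on the chance that the primary percentage is affected, since not every user would be clear at week 16.

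**Step 6: lesion counts.** Leaving out counts taken after other treatment would tend to drop subjects doing poorly on Winlevi. The mean reduction would then describe a favourable subset and would tend to be inflated. Excluding them would therefore push the lesion results in the opposite direction from the IGA rule.

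**The case against.** **The scenario needs a deviation.** Effective acne treatment added for lack of response is something Supplement I or section 5.3 rules out. The subject must depart from the protocol, stay to week 16 and then be clear, and the documents give no rate for any of these. This stands: the gap is conditional. A reader might infer that the protocol, followed as written, leads non-responders to other treatment and then credits Winlevi. The documents do not support that.

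**Withdrawal may cover it.** Section 4.3 opens its list with "The following are circumstances that would result in the subject's discontinuation from the study" and names four circumstances. Use of a prohibited drug is not one by name, so a reader might infer that such subjects must remain in the study. That goes too far. The list does not claim to be complete, and one item is an exclusion criterion becoming apparent at any time. Exclusion criterion iii in section 4.2 points to Supplement I; its wording is about wash-out, but it could arguably reach use during the study. Even on that reading, a withdrawn subject stays in the all-enrolled analysis with no stated way to score week 16.

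**Treatment policy is legitimate.** Counting outcomes whatever else was taken is a recognised choice, and section 1.1 wants to reflect everyday practice. Keeping all enrolled subjects is indeed not the fault. But the plan does not state this choice for added treatment, and it sits poorly with a protocol that prohibits these drugs and has no control arm.

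**It is a small pilot.** True: there is no success threshold, and 40% and 50% both lie within the interval around 3/10. That limits the consequence. It does not make the scoring rule unnecessary, since section 8.1 intends the data to show trends in efficacy.

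**Redaction.** A consequence of use might be stated where the text cannot be seen. The conclusion covers the visible text only.

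**Conclusion.** The point holds in a limited form. On the visible text, sections 6.1 and 8.2 score week-16 IGA for all enrolled subjects regardless of other acne treatment, while Supplement I and section 5.3 restrict that treatment. If a deviation occurs and the subject clears on the other treatment, the primary percentage rises by 10 points per such subject. The mainly upward direction assumes that the added treatment is effective. The total effect cannot be estimated, because the documents give no rate of use; the response counts and usage rates in the working are assumptions. The plan should settle the rule before the data are seen. The point does not show that the result will be biased, and it does not fault the all-enrolled principle.

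**What to change.** Add to sections 6.1 and 8.2: a subject whose section 5.3 CRF record shows a Supplement I medication, or another treatment given for facial acne, between Baseline and week 16 stays in the denominator and is counted as not achieving IGA 0/1 in the primary analysis. Report the as-observed percentage alongside and list the affected subjects.

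For the lesion reductions in section 6.2, keep all subjects in the main summary, flag counts taken after such use, and do not exclude them.

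**Cost.** A short addition to the text and no new data collection. The reported percentage may be lower. A true Winlevi responder with trivial use of another product would count as a failure; the as-observed figure and the listing make that visible. If the sponsor prefers to count outcomes regardless of other treatment, the plan should say so and still list these subjects.

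This is an analysis rule only. It proposes no change to who is withdrawn or what treatment anyone may receive.

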### 6.2 Secondary Endpoints

1. Percent of total lesion reduction at week 16 compared to baseline
2. Percent of inflammatory lesion reduction at week 16 compared to baseline
3. Percent of non-inflammatory lesion reduction at week 16 compared to baseline.
4. Tolerability measures such as, erythema, scaling, dryness, oiliness, burning/stinging and pruritus.

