#### 6.2.1 Tolerability

The Investigator will grade the current severity of erythema (disease related and/or related to IP use), dryness, peeling, and oiliness as per the following:

Score	Erythema	Dryness	Peeling	Oiliness
0 = Absent	No redness	None	Smooth	Normal
1 = Trace	Faint red or pink coloration, barely perceptible	Barely perceptible dryness by palpation with no accentuation of skin markings, skin desquamation (flakes) or fissure formation	Fine peeling, barely perceptible	Mild and localized
2 = Mild	Light red or pink coloration	Easily perceptible dryness by palpation with accentuation of skin markings but no skin desquamation (flakes) or fissure formation	Slight peeling	Mild and diffuse
3 = Moderate	Medium red coloration	Easily noted dryness with accentuation of skin markings and skin desquamation (small flakes) but no fissure formation	Definitely noticeable peeling	Moderate and diffuse
4 = Severe	Beet red coloration	Easily noted dryness with accentuation of skin markings, skin desquamation (large	Extensive peeling	Prominent and dense

The **Investigator** will **interview the subject** to determine the *current* severity of pruritus and burning/stinging; these symptoms will be graded as per the following:

Score	Description
0 = Absent	Normal, no discomfort
1 = Trace	An awareness, but no discomfort and no intervention required
2 = Mild	Noticeable discomfort causing intermittent awareness
3 = Moderate	Noticeable discomfort causing continuous awareness
4 = Marked	Definite discomfort causing continuous awareness interfering occasionally with normal daily activities
5 = Severe	Definite, continuous discomfort interfering with normal daily activities

---

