## 7 ASSESSMENTS OF SAFETY

### 7.1 Safety Assessments

Throughout the study, subjects will be monitored for signs and symptoms of adverse events. An *adverse event* is any pathological or unintended change in the structure, function or chemistry of the body that occurs during the study, irrespective of causality, including any illness, injury, toxicity, sensitivity, or sudden death. The condition must either not be present pre-study or must worsen in either intensity or frequency during the study.

A *serious adverse event* is any untoward medical occurrence, that, at any dose:

- results in death;
- is life-threatening;
- requires in-patient hospitalization or prolongation of existing hospitalization;
- results in persistent or significant disability/incapacity;
- is a congenital anomaly/birth defect; or
- is an important medical event.

An *unexpected adverse event* is any treatment-related adverse event, which is not identified in nature, severity, or frequency in current literature on the test product.

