#### 7.2.2 Adverse Event Reporting

All adverse events must be recorded by the Investigator into the CRF. The Investigator will be required to describe the adverse event, onset and stop date, severity, the course of action taken, if any, as well as any pertinent data necessary to allow a complete evaluation of the adverse event. For serious adverse events, an additional report (SAE report) must be completed.

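### Section 8.2 summarises the tolerability grades only by descriptive statistics and frequencies, which for signs present before treatment give a range, not a count, of subjects who worsened

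*Combined protocol and SAP*

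**What the plan says.** Tolerability is secondary objective 5 in section 2 and secondary endpoint 4 in section 6.2, where it reads "Tolerability measures such as, erythema, scaling, dryness, oiliness, burning/stinging and pruritus". No reference point or visit is attached to it. The lesion endpoints listed above it do carry one, for example "Percent of total lesion reduction at week 16 compared to baseline".

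Section 6.2.1 sets out the scales. "The Investigator will grade the current severity of erythema (disease related and/or related to IP use), dryness, peeling, and oiliness", each from 0 to 4. Pruritus and burning/stinging are graded from 0 to 5 by interviewing the subject. All are grades of severity at the time of the visit.

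The analysis of these grades rests on one general sentence in section 8.2: "Descriptive statistics (i.e., mean, standard deviation, etc.) will be provided for all continuous variables and frequencies for all categorical variables collected in this study". The section says that results are shown by treatment group, of which there is one, and does not mention layout by visit. It also says "All statistical tests will be two-sided and interpreted at a 5% significance level" but assigns no test to any variable. No change score, shift table or count of worsened subjects is named.

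Adverse events are handled separately. Section 7.1 sets the condition "The condition must either not be present pre-study or must worsen in either intensity or frequency during the study". Section 7.2.2 states "All adverse events must be recorded by the Investigator into the CRF". Section 8.2 adds that "The incidence and severity of adverse and/or unexpected events will be tabulated", together with a full listing.

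**The concern.** The study has one arm, so each subject's own baseline is the natural reference for deciding whether a sign got worse on treatment. A frequency table at each visit discards the pairing between visits. If a sign is present in some subjects before treatment, some may improve as the acne improves while others become irritated, and the two movements cancel in the table.

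Erythema is the clearest candidate. Its grade covers disease-related redness, and subjects enter with an acne IGA of 3 or 4 (section 4.1), so grades above zero before treatment are foreseeable. Section 8.1 says that the data are meant to reveal trends in safety as well as efficacy. The number of subjects who worsened on each item is a simple result to want from that, and it is not among the summaries named.

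**Working it through.** The plan gives no figure to reproduce. The question is whether two frequency tables determine the number of subjects who worsened.

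**Inputs.** n = 10 (section 8.1). Scales of 0 to 4 and 0 to 5 (section 6.2.1). The documents contain no tolerability data, so every grade below is assumed for illustration. Tables by visit are also assumed; this is the favourable reading of 8.2, since tables pooled over visits would show less.

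**Formula.** Take two adjacent grades. Let b subjects be at the higher grade at baseline and f at week 16. If w subjects worsened and i improved, then f = b + w − i. The tables show b and f, hence only the difference w − i. The number worsened can lie anywhere from max(0, f − b) to min(f, 10 − b).

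**Results.**

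| Case | Baseline | Week 16 | Lower limit | Upper limit |
|---|---|---|---|---|
| (a) | 5 at grade 0, 5 at grade 1 | the same | max(0, 5 − 5) = 0 | min(5, 5) = 5 |
| (b) | 8 at grade 0, 2 at grade 1 | the same | max(0, 2 − 2) = 0 | min(2, 8) = 2 |
| (c) | 3 at grade 1, 7 at grade 2 | 7 at grade 1, 3 at grade 2 | max(0, 3 − 7) = 0 | min(3, 3) = 3 |
| (d) | 10 at grade 0 | 7 at grade 0, 3 at grade 1 | max(0, 3 − 0) = 3 | min(3, 10) = 3 |

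**Means do not help.** In (c) the mean falls from (2×7 + 1×3)/10 = 1.7 to (2×3 + 1×7)/10 = 1.3. The change of −0.4 is (w − i)/10. It fits w = 0 with i = 4, and equally w = 3 with i = 7.

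**More than two grades.** Pairing the subjects in the most and least favourable ways gives the same pattern. With 4, 3, 2 and 1 subjects at grades 0 to 3 at both visits, 0 to 6 may have worsened. With 3, 3, 3 and 1 at baseline and 5, 3, 2 and 0 later, a table that improves overall, 0 to 5 may have worsened.

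**How extreme are the upper limits?** In (c) there are C(10,3) = 120 ways to choose which three subjects are at grade 2 at week 16. The number giving w worsened is C(3,w) × C(7,3 − w): 35 for w = 0, 63 for w = 1, 21 for w = 2 and 1 for w = 3. These are counts of arrangements, not probabilities, but they show that the top of the range needs an unusual pattern.

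**Reading.** The gap is real when a sign is present at baseline and vanishes when all subjects start at grade 0, as in (d).

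**The case against.** The strongest case is that the plan reports the endpoint as written. The endpoint is a list of measures, the grades describe severity at the visit, and frequencies display that directly. No section promises a count of worsened subjects. In a 10-subject open-label pilot without a formal sample size justification, leaving out one table layout biases nothing and loses no data. This largely stands, and it sets the weight of the point. The frequencies are correct as far as they go; they answer how many subjects have a grade, not how many moved up.

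The adverse event rules are also a partial substitute. Section 7.1 includes conditions that worsen relative to the pre-study state, and all events are recorded and listed. But no section ties a rise in a tolerability grade to an event record, so small rises in particular may appear in neither place.

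Some readers might infer more than this:

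- *Worsening would go unreported, or the tolerability result would be biased.* The documents do not support this. Adverse event reporting captures some worsening, and if baseline grades exist the count can be derived later from subject-level data.
- *Up to half the subjects could worsen unseen.* The 5 of 10 in case (a) is the extreme of an assumed table: it needs every grade 1 subject to improve and every grade 0 subject to worsen.
- *No baseline grade is taken.* Visit weeks are redacted in section 3, and section 5.1 shows no text in the public copy. The schedule is therefore unknown, and this is not counted against the plan.
- *The two-sided tests in 8.2 fill the gap.* None is assigned to the grades, and a test would not by itself give the number who worsened.

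**Conclusion.** The point holds as a modest gap in prespecification. For signs present before treatment, the summaries named in 8.2 bound the number of subjects who worsened but do not give it. In the assumed two-grade examples that start with the sign present, the range is 2 to 5 subjects wide out of 10. How often this arises depends on the baseline grades, about which the documents say nothing beyond allowing disease-related redness into the erythema grade.

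The conclusion rests on two assumptions: tables are produced by visit, and grades are taken at baseline. Neither can be confirmed from the public text. The priority is low.

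**What to change.** In section 8.2, for each sign and symptom graded in 6.2.1, add:

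1. a shift table of baseline grade by week 16 grade (other visits optional);
2. the number of subjects whose week 16 grade exceeds their own baseline grade, out of those with both grades;
3. optionally, an exact (Clopper-Pearson) 95% interval at week 16. It will be wide: 0 of 10 gives 0 to 30.8%, 3 of 10 gives 6.7 to 65.2%, and 5 of 10 gives 18.7 to 81.3%.

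Add a note that the erythema grade cannot separate disease-related from product-related redness, so a change in it cannot be attributed to either. Section 6.2 lists scaling where 6.2.1 grades peeling; the labels should be aligned so that the set of tables is clear.

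The cost is a few tables from grades already collected, assuming a baseline grade is taken. The tolerability picture may look less favourable, because a rise from 0 to 1 (Trace) counts as worsening; the shift table should be read beside the count for that reason.

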### **8.3 Interim Analyses**

No interim analyses will be conducted.

